7 RESEARCH QUESTION AND OBJECTIVES

7.1 Research Question

The key research questions are as follows:

- 1. What is the distribution of educational material across the markets?
- 2. What is the usage of the RM tools by HCPs and patients / caregivers?
- 3. Do HCPs and patients / caregivers understand:
 - a. The information presented in the RM tools, including:
 - i. the indicated age range,
 - ii. indicated dose,
 - b. The appropriate duration of treatment before prescribing ABILIFY, and
 - c. The identified and potential risks of concern (extrapyramidal symptoms (EPS), weight gain, somnolence, fatigue) associated with ABILIFY® for adolescent bipolar I mania indication?
- 4. Do HCPs and patients / caregivers respond appropriately to hypothetical risk scenario-based questions regarding the clinical use of ABILIFY® for the adolescent bipolar I mania indication, the identified and potential risks, and the real-world usage specifically, the recommended starting dosage and minimum recommended age of patients?

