7.2.1 Primary Objectives

The five-level RM evaluation model, shown in Figure 1, developed by Pope Woodhead, describes how effectiveness can be measured at different levels. This has been used to determine the primary objectives for the study; which will investigate the first four of these (distribution, awareness and utilisation, risk knowledge and comprehension and behaviours). The primary objectives are:

- 1. Evaluation of RM tool awareness and effective distribution (see Figure 1; levels 1 and 2): To determine the proportion of HCPs that are aware of the existence of the RM tools and how the tools were accessed (i.e. paper or electronic versions).
- 2. Evaluation of RM tool utilisation (see Figure 1; level 2):

 To determine who uses the RM communication tools, how, when they are used and how often they are used.
- 3. Evaluation of risk knowledge and comprehension (see Figure 1; level 3):

 To determine the level of knowledge and comprehension of the key risks associated with ABILIFY® when used for the treatment of adolescent bipolar I mania. The responses of HCPs and patients / caregivers will be evaluated according to their:
 - a. Knowledge of indicated age range, indicated dosage (HCPs only), and duration of treatment
 - b. Knowledge / understanding of important safety and tolerability information
 - c. Knowledge / understanding of those symptoms that require immediate contact with the treating HCP (patients / caregivers only)
 - d. Knowledge to respond appropriately to hypothetical risk scenarios (HCPs) and more simple information about identified risks (patients / caregivers)

[figure not shown]

Figure 1: Five-Level Model for Risk Minimisation Evaluation

4. Evaluation of behaviour (see Figure 1; level 4):

To evaluate HCP and patient behaviours using behavioural questions and scenarios, certain desired behaviours of HCPs and patients / caregivers will be evaluated through responses to behavioural questions as follows:

- a. Do HCPs review safety information with their patients / caregivers?
- b. Do HCPs distribute the patient information brochure to their patients / caregivers?
- c. Do HCPs educate patients / caregivers about symptoms of ADRs of concern (i.e. extrapyramidal symptoms, weight gain, somnolence, and fatigue), and about the need to report these ADRs immediately to the treating physician?

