- 1. To determine the proportion of HCPs, patients and caregivers that are aware of the existence of the RM communication tools and how these tools were accessed (i.e. paper or electronic versions).
- 2. To determine who uses the RM communication tools, and how, when and how often they are used.
- 3. To determine the level of knowledge and comprehension of the key elements of identified risks of concern associated with ABILIFY® for the adolescent bipolar I mania indication (i.e. EPS, weight gain, somnolence and fatigue).
- 4. To assess the effect of the tools on the real-world risks that the educational tools have been designed to minimise, namely the maximum starting dose of ABILIFY® for the adolescent bipolar I mania indication is not exceeded, and the minimum age of patients receiving ABILIFY® for the adolescent bipolar I mania indication is not breached.
- 5. To evaluate the HCP, patient and caregiver behaviours via behavioural questions and scenarios.

The following tables illustrate which components of the surveys will be used to carry out these evaluations:

Table 1: Demographic questions

Annex	Questions examining participant demographics
Annex 1: HCP survey	1 to 4
Annex 2: Patient survey	1 to 3
Annex 3: Caregiver survey	1 to 3

Table 2: Understanding RM tool awareness and distribution

Annex	Questions designed to understand RM tool awareness
	and distribution
Annex 1: HCP survey	7, 8, 15, 16
Annex 2: Patient survey	4, 5
Annex 3: Caregiver survey	4, 5

ABILIFY®

Table 3: Understanding RM tool use and utility

Annex	Questions designed to understand tool use and	
	utility	
Annex 1: HCP survey	9 to 14, and 17 to 23	
Annex 2: Patient survey	6 to 11	
Annex 3: Caregiver survey	6 to 13	

For this survey, the intention is to primarily test knowledge indirectly, as meeting behavioural goals will require some degree of working-knowledge of ABILIFY[®] benefits and risk, when used for the adolescent bipolar I mania indication.

Tables 4 and 5 contain the questions that reflect understanding of how to take ABILIFY[®], how to treat ADRs (HCPs), and awareness of risks and what to do if risks are identified (patients / caregivers).

Table 4: Understanding knowledge of RM tool content

Annex	Questions designed to understand knowledge of tool	
	content	
Annex 1: HCP survey	24 – 35	
Annex 2: Patient survey	12 – 33	
Annex 3: Caregiver survey	14 – 35	

Table 5: Knowledge of potential or identified risks of concern

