HCPs will be expected to complete the surveys within one month of being recruited. Patient and caregiver recruitment will occur through the HCPs. To ensure an unbiased sample, up to three patients / caregivers can be recruited through a single HCP. It is, however, expected that most HCPs will recruit one or two patients / caregivers only. The prescribing physician will recruit consecutive patients / caregivers, and informed consent (via a letter provided as part of the recruitment process) will be taken once potential participants are randomly selected from the HCP lists submitted to PW. Assent will be taken from paediatric patients who are not old enough to give informed consent, and appropriate consent will be taken from parents / carers, as appropriate.

In order to minimise bias of selecting compliant patients, PW will randomly identify actual participants from lists of patients supplied by HCPs. A similar quota based methodology as used in HCP selection will be employed when recruiting patients and caregivers (e.g. recruitment continues until the target quota has been reached or exceeded). Patients and caregivers will be provided with an invitation letter (containing informed consent, and details of the survey and how to participate) through their HCP. The HCP will pass contact details of those patients and caregivers agreeing to take part to PW who will provide unique IDs and the web-link to a patient survey).

The Patient / Caregiver surveys will be answered either whilst the patient is still receiving ABILIFY® or within 2 months of receiving their last dose (this is to reduce risks of patients / carers not being able to recall aspects of treatment and use of the RM tools), and within 1 month of being recruited.

Question 3 in the Patient / carer survey asks how long the patient was treated for, and if they are still being treated. Question 2 asks how old the patient was at treatment initiation. PW will also administer the web questionnaires and collect results from the patients and caregivers.

A total sample size of 148 to 158 HCPs and 148 to 158 patients / caregivers, as discussed below, will be met.

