8.3 Variables

Variables of interest and their definition include:

• Age of patient

Defined as the age of the patient at treatment initiation

Dose

Defined as the most recent dose taken before completing the survey

• Treatment duration

Defined as the length of time since the first dose taken for this indication, irrespective of whether treatment is continuous or interrupted

• HCPs' experience using ABILIFY® for the adolescent bipolar I mania indication
Defined as how many the HCP has treated with ABILIFY® for moderate to severe manic
episodes in bipolar I disorder in adolescents aged 13 years and older

• Usage of tools

Defined as whether the respondent has used the RM tools on one or more occasions

• Medical specialty

Defined as: psychiatrist, child / adolescent psychiatrist, nurse or prescriber

• Country

Country where the HCP or patient / caregiver resides

The key survey effectiveness evaluation metrics are shown in Table 7. Questions designed to measure: demographics, awareness and distribution, use and utility, knowledge of tool content, knowledge of identified or potential risks of concern and behaviours are described in Section 9.1.1.

ABILIFY®

Table 7: Key effectiveness evaluation metrics

_	Target Audience	
Metrics	НСР	Patient / Caregiver
Awareness of tools	X	X
Utilisation of tools	X	X
Knowledge and comprehension		
Symptoms requiring physician notification	X	X
Recommended age	X	N/A
Indicated dose	X	N/A
Indicated treatment duration	X	X
Risks of		
• EPS	X	X
 Weight gain 	X	X
 Somnolence 	X	X
• Fatigue	X	X
Ability to respond correctly to hypothetical	X	X
risk scenarios		
Behaviour		
Reviewing safety information with	X	
Patients / Caregivers		
Monitor for ARs and appropriate action if	X	
ADR is identified		
Distribution of Patient information	X	X
brochure to Patients / Caregivers		
Educating Patients / caregivers about	X	X
symptoms of EPS, weight gain,		
somnolence and fatigue and need to report		
them to a physician		

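### The item map gives patients and caregivers no knowledge item for indicated treatment duration, although objective 3a and Table 7 make it a knowledge metric for them

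*Protocol*

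**What the plan says.** Research question 3 (Protocol section 7.1) opens with "Do HCPs and patients / caregivers understand" and lists age range, dose and duration among its sub-items. Primary objective 3 (section 7.2.1) covers the same respondents: "The responses of HCPs and patients / caregivers will be evaluated according to their", followed at item (a) by "Knowledge of indicated age range, indicated dosage (HCPs only), and duration of treatment". The restriction to HCPs is attached to dosage only.

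Table 7 (section 8.3), under knowledge and comprehension, has a row "Indicated treatment duration" marked X for both HCPs and patients/caregivers. The adjacent rows for recommended age and indicated dose are N/A for patients/caregivers.

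Table 5 (section 8.1) maps each topic to survey questions. For duration, the patient/caregiver entry is Question 3 alone, labelled indirect. Section 8.2.2 describes that item: "Question 3 in the Patient / carer survey asks how long the patient was treated for, and if they are still being treated". Table 1 places it among the demographic items ("Annex 2: Patient survey 1 to 3", with the same range for caregivers). Table 4 gives the knowledge items as "Annex 2: Patient survey 12 – 33", and 14 to 35 for caregivers.

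**The concern.** A knowledge metric needs an item whose answer can be judged right or wrong. The length of time a patient was treated cannot be judged that way. It depends on the prescriber, the course of the illness and the date of the survey. Two respondents with the same treatment length may differ completely in whether they know the indicated duration. Section 8.2.2 also admits patients who are still on treatment, so some answers will be incomplete durations.

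Effectiveness is defined in section 7.2 to include knowledge, and section 6 says the results go to the EMA and may lead to changes in the risk management plan. If the map is followed, one result declared under a primary objective is either absent or has to be filled with an exposure measure.

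**Working it through.** The protocol states no figure on this point to reproduce. The check sets its statements side by side and compares item numbers.

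**Where Question 3 sits**
- Demographic items (Table 1): 1 to 3 in both surveys. Question 3 is inside.
- Knowledge items (Table 4): patients 12 to 33, caregivers 14 to 35. Question 3 is outside both.
- Section 8.3 defines the treatment-duration variable as time elapsed since the first dose for this indication, which is exposure.

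**Which knowledge items Table 5 uses**
- Patients: dose 12–17 (6 items), weight gain 19–23 (5), EPS 24–26 (3), fatigue 27–29 (3), somnolence 30–32 (3). Mapped: 6 + 5 + 3 + 3 + 3 = 20. The Table 4 block holds 33 − 12 + 1 = 22. The two without a row in Table 5 are 18 and 33.
- Caregivers: dose 14–19, weight gain 21–25, EPS 26–28, fatigue 29–31, somnolence 32–34. Again 20 of 35 − 14 + 1 = 22 are mapped. The two without a row are 20 and 35.
- Knowledge-block items assigned to duration: 0 in each survey.

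**Patient/caregiver scope by topic**

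| Topic | Research question 3 | Objective 3a | Table 5 | Table 7 |
|---|---|---|---|---|
| Duration | included | included | Question 3 only, indirect | X |
| Dose | included | HCPs only | 12–17 / 14–19, indirect | N/A |
| Age | included | included | demographic age only | N/A |

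The rows fail in different ways. For duration, a metric is claimed and no knowledge item is assigned. For dose, items are assigned while objective 3a and Table 7 exclude the metric. For age, the research question and the objective include patients/caregivers, Table 7 excludes them, and Table 5 has only a demographic proxy.

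**Respondents affected**
The planned patient/caregiver sample is 148 to 158. The country quotas in section 8.5 sum to 6 × 13 + 6 × 12 = 150. This is the number of people for whom the cell has no mapped knowledge item. It does not measure bias.

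**The case against.** The strongest reply is that Table 5 openly calls the mapping indirect, and section 8.1 says knowledge is to be tested mainly by indirect means. The age row of Table 5 explains such a proxy: it may show whether prescribing is appropriate. Question 3 could serve the same purpose. That is a fair reading of Question 3, but it does not rescue the Table 7 entry. For age, where the proxy is of the same kind, Table 7 sets patient/caregiver knowledge to N/A; for duration it keeps the X. A check on prescribing is not a measure of what the respondent understands, and an analysis plan cannot recover knowledge from an item that does not ask for it.

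Three stronger readings are tempting, and the protocol does not support them.
- A reader might infer that no duration-knowledge result can exist. The patient and caregiver questionnaires are withheld. Patient Questions 18 and 33 and caregiver Questions 20 and 35 are knowledge items with no row in Table 5, and section 8.1 relies on Tables 4 and 5 together. A duration question among the items not shown cannot be excluded.
- A reader might infer that treatment length will be reported as knowledge. Nothing in the protocol says that Question 3 will be scored.
- A reader might infer that dose has the same fault and is unanswerable. Its conflict runs the other way: items exist, and objective 3a and Table 7 agree with each other in excluding the metric. What is left is a scope conflict with research question 3 and Table 5.

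It is also true that the analysis is descriptive and that this is one cell among many in Table 7.

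**Conclusion.** The concern holds for the item map as written. Knowledge of the indicated duration is declared for patients and caregivers under a primary objective, and the single item mapped to it records treatment history. The extent is one Table 7 metric with no mapped knowledge item in either survey. No numerical bias can be attached to it.

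The conclusion rests on the description of Question 3 in section 8.2.2 and on the numbering in Tables 1, 4 and 5. If the withheld questionnaires contain a duration-knowledge item, the defect reduces to a wrong reference in Table 5, which still needs correcting. The dose and age inconsistencies are separate matters of scope. The point should be settled before survey content is finalised, but it does not threaten the study as a whole.

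**What to change.** For duration, choose one:
- Name in Table 5 an existing knowledge item on indicated duration or, if there is none, add one to each of the patient and caregiver surveys. Score it against the product information, with the correct answer fixed in advance. It should ask what the respondent understands. What the respondent was told would measure HCP education.
- Set the patient/caregiver duration cell in Table 7 to N/A, and limit objective 3a and research question 3 to HCPs for duration.

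Under either choice, remove Question 3 as the Table 5 knowledge entry and report it only as treatment history.

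In the same edit, state one patient/caregiver scope for dose and one for age, and carry each through research question 3, objective 3a, Table 5 and Table 7. Make the matching change in the abstract (section 3.3.1).

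The cost is at most one extra question in each of two surveys, or wording changes alone. No extra respondents are needed. The milestones in section 5 place survey content finalisation in Q1 2014, after the protocol date of 15 October 2013, so the change fits the planned schedule.

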8.2.3 Honorarium

HCPs will be contracted to complete the HCP survey and to encourage patients / caregivers to participate in surveys. For this work, and the time involved, HCPs will be offered a market rate and specific country specific honorarium. (confirmed honorarium will be added at a later date) Rates may be adapted if Otsuka standard honoraria fees or policies change during the execution of the surveys. Patients / caregivers will not receive honoraria.

8.2.4 Exclusion Criteria

HCPs will be excluded from the survey if they are not involved in the treatment of patients using ABILIFY for the adolescent bipolar I mania indication.

Protocol Number: 31-13-300 ABILIFY®

8.3 Variables

Variables of interest and their definition include:

• Age of patient

Defined as the age of the patient at treatment initiation

Dose

Defined as the most recent dose taken before completing the survey

• Treatment duration

Defined as the length of time since the first dose taken for this indication, irrespective of whether treatment is continuous or interrupted

• HCPs' experience using ABILIFY® for the adolescent bipolar I mania indication
Defined as how many the HCP has treated with ABILIFY® for moderate to severe manic
episodes in bipolar I disorder in adolescents aged 13 years and older

• Usage of tools

Defined as whether the respondent has used the RM tools on one or more occasions

• Medical specialty

Defined as: psychiatrist, child / adolescent psychiatrist, nurse or prescriber

• Country

Country where the HCP or patient / caregiver resides

The key survey effectiveness evaluation metrics are shown in Table 7. Questions designed to measure: demographics, awareness and distribution, use and utility, knowledge of tool content, knowledge of identified or potential risks of concern and behaviours are described in Section 9.1.1.

ABILIFY®

Table 7: Key effectiveness evaluation metrics

_	Target Audience	
Metrics	НСР	Patient / Caregiver
Awareness of tools	X	X
Utilisation of tools	X	X
Knowledge and comprehension		
Symptoms requiring physician notification	X	X
Recommended age	X	N/A
Indicated dose	X	N/A
Indicated treatment duration	X	X
Risks of		
• EPS	X	X
 Weight gain 	X	X
 Somnolence 	X	X
• Fatigue	X	X
Ability to respond correctly to hypothetical	X	X
risk scenarios		
Behaviour		
Reviewing safety information with	X	
Patients / Caregivers		
Monitor for ARs and appropriate action if	X	
ADR is identified		
Distribution of Patient information	X	X
brochure to Patients / Caregivers		
Educating Patients / caregivers about	X	X
symptoms of EPS, weight gain,		
somnolence and fatigue and need to report		
them to a physician		

8.4 Data Sources

The survey will include web-based structured questionnaires comprised of mostly multiple choice questions with some descriptive comments sections.

The surveys will determine:

- 1. General awareness of tools
- 2. When and how often the tools are used
- 3. If paper-based or web-based tools (downloads) are used

- 4. If HCPs use the tools themselves, if they give the PCIB to their patients / caregivers, and how and when they use the tools with Patients / Caregivers
- 5. If patients / caregivers received their PCIBs and if they use them
- 6. If the RM tools can be improved based upon feedback or proposals from HCPs, patients and caregivers
- 7. Knowledge and understanding of the specific ADRs associated with ABILIFY presented in the RM tools
- 8. If the tools promote appropriate behaviours (e.g. do physicians or other HCPs understand how to manage patients that may be experiencing ADRs and do Patients / Caregivers know what actions to take if they suspect they are suffering an ADR?)

For data protection, the identities of HCPs, Patients and Caregivers will be controlled by the use of unique identification codes provided to the participants by PW. The source ID numbers will be held securely on a separate system from that used to host the survey applications. This data will be used solely for the purpose of identifying whether the HCP, patient or caregiver has completed the survey.

Survey participants will be informed in the recruitment correspondence that the survey needs to be completed in a single sitting and that sufficient time (c.25 min for HCP s and c.15-20 min for the patients) needs to be set aside to complete the surveys. In the case of HCPs, the payment of the honoraria is contingent on completing the survey in this single sitting. This is to prevent users revising or studying for answers and using several sessions to answer a survey, thus reducing the possibility of biasing the survey by users answering the survey on multiple occasions.

The survey will be timed out after 20 minutes of continuous inactivity (e.g. user not interacting with the web-based survey for more than 20 minutes), which will also reduce the chances that participants consult reference sources. If users do not complete the surveys, their data will not be analysed and new participants will be sought.

8.5 Study Size

The sample size will be driven by the estimated size of the population receiving ABILIFY[®] for the adolescent bipolar I mania indication. The sample size is based on an acceptable margin of error of less than 20% in the population of interest. This will yield between 148 to 158 HCPs and 148 to 158 patients / caregivers once the final evaluation has been completed.

The calculation to determine sample size was performed using a sample size calculator available from Raosoft⁽⁶⁾, and incorporated margins of error by country; hence, the range of 148 to 158 HCPs and 148 to 158 patients / caregivers. The calculation of sample sizes is described in Section 9.7.2.

To achieve a representative population of HCPs relevant to the local clinical practice of the country (e.g. nurses, ancillary HCPs and prescribers), and patients and caregivers, and to attain the ranges outlined above, approximately 20 to 30% of the actually prescribing / treating HCP

population would need to be invited as part of the recruiting process. For example, in the UK (estimated HCP population of 2188), a confidence level of 95% and 85% of correct responses to a knowledge based question, and a sample size of 13 HCPs, gives a margin of error of 19.36% (see Table 9).

It should be noted that ABILIFY[®] used in this indication is considered an area of specialised medicine. It is expected that some countries will have few prescribers, especially so since the product will not be actively promoted for use in the paediatric / adolescent population. The actual numbers surveyed will depend on the specific numbers of centres and HCP users. These values may be adjusted accordingly if there are particularly high or low national usages of ABILIFY[®] for the adolescent bipolar I mania indication at the time of the survey.

The following numbers of HCPs, and Patients or carers will be included per country:

UK	13 HCPs and 13 Patients / caregivers
Germany	13 HCPs and 13 Patients / caregivers
Spain	13 HCPs and 13 Patients / caregivers
Italy	13 HCPs and 13 Patients / caregivers
Sweden	13 HCPs and 13 Patients / caregivers
Denmark	13 HCPs and 13 Patients / caregivers
Norway	12 HCPs and 12 Patients / caregivers
Ireland	12 HCPs and 12 Patients / caregivers
Austria	12 HCPs and 12 Patients / caregivers
Portugal	12 HCPs and 12 Patients / caregivers
Cyprus/Greece	12 HCPs and 12 Patients / caregivers
Slovenia	12 HCPs and 12 Patients / caregivers

These countries will be surveyed during $Q1/2\ 2014$ (assuming the protocol is approved before this).

The study will be registered on ENCEPP within one month of obtaining CHMP / PRAC approval of the study protocol.

